3.5 Analysis Populations

All safety analyses will be based on the Safety population that will comprise all patients who signed the inform consent and received at least one dose of study medication. The remaining analyses, including the baseline profile of the patients and treatment effectiveness, will be based on the Intent-to-Treat (ITT) population that will comprise all patients who signed informed consent, meet the inclusion / exclusion criteria, and received at least one dose of study medication.

3.6 Patient Disposition and Discontinuation

The number of patients who are enrolled and who have completed each visit will be reported, including all post-enrolment discontinuations, for the total cohort and by treatment group.

COMPLETE - PS Statistical Analysis Plan Version 3.0 July 23rd, 2015 Page 27 of 231

In addition to an overall summary of early discontinuations and the associated reasons, the time to discontinuation since the baseline visit will be evaluated using life table methods. The following data will be presented:

- 1. The number and percentage of subjects who completed or discontinued prematurely from the study overall and for each scheduled visit.
- 2. The number and percentage of subjects who discontinued for each reason.
- 3. Time to event methods will be used to estimate survival/discontinuation. Mean and median time to discontinuation (with 95% CI) will be tabulated.

### 3.7 Treatment Exposure and Dosing

Treatment exposure will be calculated in terms of number of months exposed to topical agents, traditional systemic agents and adalimumab using the following formula:

Exposure (months) = 
$$\frac{\text{(Last Date of Dosing - First Date of Dosing + 1)}}{30.4}$$

In this formula, the value 30.4 corresponds to the average number of days within a month over the course of a year. The last date of dosing might not be known and so the visit date will be used.

The following information will be presented for the total study population: sample size, mean, median, SD, minimum, maximum, and 95% confidence interval.

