#### **Patient Discontinuation from the Study:**

Patients could be withdrawn from the study at any time by the treating physician or on their own accord. Patients that participate in another trial will be withdrawn from the study. Patients that terminate treatment or switch from their current treatment will be followed for the 24 month study follow up period. Patients may change treatment at the discretion of the physician including switching from one of the defined treatment cohorts to another. Lack of therapeutic response, low compliance to treatment or the incidence of adverse events will not necessitate study withdrawal.

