### 2.4 Study Design

JSS Recherche médicale Medical Research

COMPLETE - PS Statistical Analysis Plan Version 3.0 July 23rd, 2015

Page 13 of 231

This is a Canadian Post Marketing Observational Study (PMOS) utilizing a prospective cohort design. Patients are entered into the study cohort at the time of change of their PS treatment for any reason and are followed for a maximum of 24 months with recommended assessments at 3, 6, 12, 18 and 24 months after baseline. Treatment of the patients and follow up will be according to the physician's judgment, regional regulations and the product monograph. Off-label use will not be permitted and these patients will not be included in the study. Dose changes including escalation will be allowed as per the physician's judgment for

There will be 660 patients enrolled from the practices of approximately 30 - 40 dermatologists across Canada. The study sample will be randomly selected and proportional to the Canadian population and distribution of dermatologists in Canada.

patients that were treated as per indication when they were enrolled in the study.

The following patient cohorts will be defined:

- 1. Initiated treatment with a new topical agent that was not used before or already on treatment with a topical agent and not responding requiring a change of treatment type, frequency or dose.
- 2. Initiated treatment with a new systemic agent that was not used before alone or in combination with topical agents.
- 3. Initiated on treatment with adalimumab alone or in combination with topical agents.

In the case that the patient is switched from one cohort to another during the course of the study, follow up will continue as per the study protocol. For these cases, the treatment will be considered as a time dependent variable in the assessment of the study outcomes. In

JSS Recherche médicale Medical Research

**COMPLETE - PS Statistical Analysis Plan** Version 3.0

July 23rd, 2015

Page 14 of 231

addition, depending on the number of patients switching cohorts, separate cohorts may be

defined to include those patients that change treatment during the study.

Effectiveness outcome measures will include changes in clinical outcomes and quality of

life. Health economic assessments will be conducted to determine the impact of treatment on

PS related burden of illness. The impact of PS and the different treatment approaches on

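### The single first-to-last dosing span in SAP 3.7 counts time off treatment as exposure and leaves the first date and the fallback visit undefined

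*SAP*

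**What the plan says.** SAP 3.7 sets the scope: "Treatment exposure will be calculated in terms of number of months exposed to topical agents, traditional systemic agents and adalimumab". The numerator is "Last Date of Dosing - First Date of Dosing + 1". The divisor is explained by the statement that "the value 30.4 corresponds to the average number of days within a month over the course of a year". For missing dates the section adds: "The last date of dosing might not be known and so the visit date will be used". For presentation it says: "The following information will be presented for the total study population: sample size, mean, median, SD, minimum, maximum, and 95% confidence interval".

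The section does not say whether the first date is the first dose on or after baseline or the first dose ever. It does not say what happens when dosing is interrupted and resumed, or which visit supplies the substitute date.

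Three features of the design bear on this:

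- SAP 2.4 admits to cohort 1 not only patients who start a new topical but also those "already on treatment with a topical agent and not responding requiring a change of treatment type, frequency or dose". Cohorts 2 and 3 may use topicals in combination.
- Protocol 6.5.1, on discontinuation, states: "Patients that terminate treatment or switch from their current treatment will be followed for the 24 month study follow up period". It also lets the physician move a patient from one treatment cohort to another.
- SAP 3.11 treats treatment as a time-dependent covariate in the secondary analyses.

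**The concern.** A first-to-last span measures time on treatment only if dosing is continuous between the two dates. This study expects the opposite for some patients: they may stop or switch at the physician's discretion and remain under observation. If a patient later returns to the same class, the span runs across the interval away from it. If the patient was on another class in that interval, the same months are credited to both. (Overlap from true combination therapy is legitimate; overlap created by an unrecognised gap is not.)

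The first date raises a separate question. A cohort 1 patient whose topical is changed only in dose or frequency may have begun that agent well before enrolment. The same can be true of a topical carried on alongside a systemic agent or adalimumab. With no anchor at baseline, two programmers could follow the SAP and report different figures for the same patient.

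At stake is the accuracy of a planned output, Table 3 in the SAP's list of tables. It describes how long patients were treated in a study that also compares the safety of the three treatments.

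**Working it through.** **The plan's own constant.** 365/12 = 30.417 and 365.25/12 = 30.4375. Both round to 30.4, so the divisor reproduces.

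**Inputs.** The formula is from SAP 3.7, and the 24-month follow-up and recommended visits at 3, 6, 12, 18 and 24 months are from SAP 2.5. The documents give no lengths for treatment gaps or for pre-study use, so every such length below is an assumption chosen for illustration.

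**Continuous dosing from baseline.** First dose on day 0, last on day 730: (730 − 0 + 1)/30.4 = 731/30.4 = 24.0 months. The formula is right.

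**Gaps.** First and last doses as above, with one gap inside the span. The formula always returns 24.0.

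| Assumed gap | Days | Months on treatment | Formula / on treatment |
|---|---|---|---|
| 1 month | 30 | 701/30.4 = 23.1 | 1.04 |
| 3 months | 91 | 640/30.4 = 21.1 | 1.14 |
| 6 months | 183 | 548/30.4 = 18.0 | 1.33 |
| 12 months | 365 | 366/30.4 = 12.0 | 2.00 |

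**Switch and return.** Class A on days 1–180 and 540–730, class B on days 181–539.

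- Class A by the formula: (730 − 1 + 1)/30.4 = 24.0 months.
- Class A on treatment: (180 + 191)/30.4 = 371/30.4 = 12.2 months.
- Class B by the formula: (539 − 181 + 1)/30.4 = 359/30.4 = 11.8 months, which is correct.
- Sum over classes: (730 + 359)/30.4 = 35.8 months, in a patient observed for 24.0 months and never on two classes at once.

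A patient who leaves a class for good, with a known last dose, is not affected. The error needs a return to the class.

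**First date before baseline.** This applies only if the first date is read as first-ever use. With last dose on day 730:

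- 3 months (91 days) of prior use: 822/30.4 = 27.0 months.
- 6 months (183 days): 914/30.4 = 30.1 months.
- 12 months (365 days): 1,096/30.4 = 36.1 months, against 24.0 on study (ratio 1.50).

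If the date is read as the first dose on study, the excess is zero.

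**Substituted visit date.** If the visit used falls 30, 91 or 182 days after the true last dose, it adds 30/30.4 = 1.0, 91/30.4 = 3.0 or 182/30.4 = 6.0 months. The longest case corresponds to the six-month spacing of recommended visits after month 6. A visit before the true last dose would take months away instead.

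**The case against.** The strongest reply is that a reader might infer more from the formula than the SAP says, in four respects.

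- **Pre-study topical use is counted.** This is not established. SAP 3.5 defines its populations by receipt of study medication, and SAP 3.6 times discontinuation from the baseline visit. SAP 3.8.2 summarises previous psoriasis drugs separately, and they have their own table (Table 7). All of this favours reading the first date as an on-study date. The reply stands: SAP 3.7 permits the wider reading but does not require it.
- **Every reported month is wrong, most of all for topicals.** For a patient with a baseline start and no gap the formula is exact. Topicals are the class most open to a pre-baseline date, but nothing shows that gaps are longer or commoner with them.
- **Topicals would look safer per month of exposure.** No such rate is planned. SAP 2.10.2 assesses safety by incidence, Protocol 10.2 compares groups by adjusted relative risks, and no listed table is an exposure-adjusted rate.
- **The visit-date rule inflates exposure.** Its direction is unknown because the visit is not named. Data from unscheduled visits are also recorded, which can shorten the interval.

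On presentation, SAP 3.7 does not say that only totals will be shown, and SAP 3.1.1 calls for the size of each treatment group in table column headings. The layout and footnotes of mock Table 3 are not in the text examined, so a definition or cohort columns there cannot be ruled out.

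None of this answers the point about gaps. That follows from the formula as written, whichever way the first date is read.

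**Conclusion.** The point holds in a limited form. Followed exactly, SAP 3.7 reports time off a class as exposure whenever a patient leaves that class and returns. A six-month gap turns 18.0 months into 24.0 (+33%), and the switch-and-return example turns 12.2 into 24.0. These gap lengths are assumed, so the average effect in this study cannot be derived.

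The undefined first date and the unnamed visit are ambiguities, not demonstrated errors. The first could add pre-study months, chiefly for topicals; the second could move exposure either way.

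The consequence is an inaccurate descriptive table. The documents do not use exposure as a denominator, so neither the primary comparison nor the planned safety comparison changes. The correction is worth making because the rule is explicit, gives a wrong figure in a situation the protocol allows, and is easily replaced.

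**What to change.** Replace the span with on-study exposure per agent class, summed over treatment episodes:

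Σ [min(stop date, last study date) − max(start date, baseline or enrolment treatment-change date) + 1] / 30.4

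Merge overlapping episodes within a class before summing, so that two topicals used together are not counted twice. Name the visit or imputation used for an unknown stop date, and flag those values as imputed. Show exposure by treatment cohort as well as in total. Leave pre-study use in the prior-medication summaries.

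The cost is a revised SAP paragraph and extra programming. The method relies on start and stop dates for each episode. Protocol 6.5.1 mentions dose, frequency, duration and route of psoriasis treatment before and during the study, but does not expressly mention episode dates. The time-dependent treatment analysis in SAP 3.11 already needs that information, so the fix should add no new data requirement; the sponsor should confirm that the dates are captured.

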## 3.8 Subject Demographics and Baseline Characteristics

Descriptive statistics consisting of the mean, median, standard deviation and 95% confidence interval of the mean for continuous scale variables and frequency distributions for categorical variables will be produced for the baseline characteristics. These descriptive

COMPLETE - PS Statistical Analysis Plan Version 3.0 July 23rd, 2015 Page 28 of 231

statistics will be produced for the study cohort as a whole and for the three treatment cohorts as described in section 2.4, and by Canadian regions.

Between-group differences with respect to baseline characteristics will be assessed for statistical significance with One Way Analysis of Variance (ANOVA) for continuous variables if normally distributed or the Kruskal Wallis test if not normally distributed, and the Chi-Square statistic or the Fisher's exact test for categorical variables. Variables for which a trend for statistical significance (P<0.15) or clinically important difference (more than 2–fold) is observed will be considered as potential confounders and will be included as covariates in the multivariable analyses or propensity score development described in the following sections.

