of illness. The design is that of a prospective observational study with its inherent biases including confounding by indication. Statistical methods including multi-variate models and propensity scores will be used to adjust between group differences with respect to prognostic baseline characteristics. Mixed effects models will be incorporated to compensate for unequal follow up and lack of precisely scheduled visits. The design and statistical analysis employed are therefore required and appropriate to produce a valid real – life assessment and comparison of the different modes for the management of psoriasis that are currently used in Canada.

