#### 6.2 Number of Patients to be Enrolled

A total of 660 patients will be enrolled in the current study from the practices of 30-40 dermatologists. A maximum of 30 patients per site will be allowed. Recruitment will be over a 24 month period. In order to provide adequate power to assess the effect of different treatment modalities, it will be recommended that 50% of the patients from each site will be initiated on treatment with adalimumab.

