#### 10.2 General Considerations:

Descriptive statistics consisting of the mean, median, standard deviation and 95% confidence interval of the mean for continuous scale variables and frequency distributions for categorical variables will be produced for the baseline characteristics. These descriptive statistics will be produced for the study cohort as a whole and for the three treatment cohorts as described in section 6.0.

Between cohort differences with respect to the baseline parameters will be assessed with the Chi-Square statistic for categorical variables and One Way Analysis of variance (ANOVA) for continuous scale variables. Variables for which a trend for statistical significance (P < 0.15) or clinically important difference (more than 2 - fold) are observed will be considered as potential confounders and will be included in the multivariate analyses or propensity score development described later. Descriptive statistics will be produced for all variables and the changes from baseline when Statistical Methods to Address the Study Objectives:

Between group differences with respect to achieving the primary effectiveness outcome, specifically a PGA of "0" or "1" at 24 months will be assessed with simple logistic regression analysis and multivariate logistic regression models adjusting for potential confounders or the propensity score. A more relevant analysis will be to assess the differences between the groups with respect to the time to achieving the end point. For this analysis Kaplan Meier based time to event (survival) analysis will be used with the log-rank test to assess the statistical significance of the between group differences. Cox's proportional hazards model will also be used to adjust for potential confounders or the propensity score.

Between groups differences with respect to the changes in the BSA, PGA, DLQI, Psoriasis

Related Pruritus Assessment VAS, Plaque Psoriasis and Psoriatic Arthritis Pain VAS, BDI,9SF-12 (second version) WLQ from baseline to 24 months of treatment will be assessed with One Way ANOVA or repeated measures, mixed effects general linear model adjusting for potential confounders or the propensity score. Planned contrasts will be used to assess between group differences at the other follow up time points. Pairwise between group comparisons will be adjusted for multiplicity with the Tukey's Least Significance Test.

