#### 10.3 Sample Size Calculations

Sample size considerations are based on the primary objectives of the study, specifically the proportion of patients that achieve a PGA rating of "0" or "1" at 24 months of follow up.

The following data and assumptions were used to determine the sample size requirements for the study:

- In the Champion study after 16 weeks of treatment 73% of the patients treated with adalimumab, 30% of the patients treated with methotrexate and 11.3% of the patients treated with placebo achieved PGA values of 0 or 1 indicating clear or minimal disease.
- The Champion study was a randomized placebo controlled clinical trial that was based on a strict protocol not allowing any concomitant treatment and enrolling a very well defined patient population. In the current study we can assume that we will observe similar trends in the order of treatment effectiveness, by which adalimumab will be superior to traditional systemic agents, which will be superior to topical agents. However, due to case mix and use of concomitant medications the actual therapeutic effect and difference between groups may be more variable and lower than that observed in the CHAMPION study. We can therefore assume that due to patient profile, and in order to be conservative, that the observed proportion of patient achieving and maintaining a PGA≤ 1 at 6 months will be approximately 50%. A relative reduction of 20% (RR = 0.80) in PGA would be considered as the minimum acceptable for clinical importance. Therefore, the current study we should be powered to detect a 20% relative reduction between adalimumab and traditional systemic agents, and a similar difference between systemic and topical agents. It follows that if we assume that the proportion of patients treated with adalimumab that achieve PGA ≤1.0 at six months will be

50%, the proportion in the patients treated with traditional systemic agents will be 40% ( $\underline{RR}$ =0.8) and that in patients treated with topical agents will be 32% ( $\underline{RR}$  = 0.8).

• For an expected treatment group ratio of 1:1 for adalimumab: traditional systemic agents and topical agents a total of 360 (180: 180) patients will be required for 80% power and two tailed significance of 5%. Assuming a 25% attrition rate and allowing for 100 additional patients (10 per variable) in the multivariate analysis 660 (330:165:165) patients will be recruited.

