## 3 Statistical Methods

## 3.1 Statistical Handling Policy

### 3.1.1 Analysis Conventions

This section details general guidelines to be used for the statistical analyses. Deviations from these general policies may be given in the specific detailed sections of this statistical analysis plan. When this situation occurs, the rules set forth in the specific section take precedence over the general conventions. The following policies will be applied to all data presentations and analyses:

- Two-tailed tests will be performed for all analyses that use statistical testing with a significance level of  $\alpha = 0.05$ .
- All p-values will be rounded to 3 decimal places. All p-values that round to 0.000 will be presented as '<0.001' and p-values that round to 1.000 will be presented as '>0.999'. Any p-value  $\leq$ 0.05 will be considered statistically significant.
- Summary statistics will consist of the number and percentage of responses in each category for discrete variables, and the mean, median, standard deviation (SD), minimum, maximum, and 95% confidence interval for continuous variables.

COMPLETE - PS Statistical Analysis Plan Version 3.0 July 23rd, 2015 Page 24 of 231

- All mean and median values will be formatted to one decimal place. Standard deviation values will be formatted to two decimal places.
- All percentages will be rounded to one decimal place. Where appropriate, the number and percentage of responses will be presented in the form XX (XX.X %), where the percentage is in the parentheses.
- All listings will be sorted for presentation in order of treatment group, site number, subject number, and date of procedure or event.
- When necessary for analysis purposes, partial dates will be completed (i.e., turned into complete dates) using the most conservative approach. Where appropriate, all analysis and summary tables will have the population sample size for each treatment group in the column heading.
- All analyses and summary tables will have the population sample size for each treatment group in the column heading.
- Tables will include footnotes describing the analyses involved, and listings of covariates included in the analyses, where relevant.

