### 3.2 Bias by Indication

One of the most important challenges in conducting between treatment comparisons in observational or naturally occurring experiment studies is confounding by indication. This occurs because the patients are allocated to different treatment groups not randomly but on the basis of the treating physician's judgment. This may result in an imbalance of the prognostic profile between the treatment groups and therefore confounding in the assessment of differences with respect to the study outcome measures. Multi-variable models that include potential confounders as covariates or propensity scores developed with potential confounders are valid solutions for the statistical adjustment of between group baseline differences and minimization of bias. The development of the propensity score will be based on categorical or multinomial logistic regression and binary logistic regression for the assessment of the profile differences between patients treated with adalimumab, topical agents and traditional systemic agents. Stratification of the analyses into homogeneous subgroups is another solution. All of these solutions will be explored in the current study. Unfortunately determination of the appropriate approach is data driven and cannot be determined a-priori.

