## 3.10 Analysis of the Primary Objective

For the primary objective, between-group differences with respect to achieving a PGA of "0" or "1" at six months will be assessed with simple logistic regression analysis and multivariate logistic regression models adjusting for potential confounders or the propensity score. In addition, a Generalized Estimating Equation (GEE) model will be used to compare

COMPLETE - PS Statistical Analysis Plan Version 3.0 July 23rd, 2015 Page 30 of 231

the three patient groups in terms of achieving a PGA of "0" or "1" over 24 months of treatment. Kaplan Meier based time to event (survival) analysis will be used with the log-rank test to assess the statistical significance of the between group differences. Cox's proportional hazards model will also be used to adjust for potential confounders or the propensity score.

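### Baseline PGA is not guaranteed a place in the adjusted 6-month model: the only stated entry rule is a test of cohort imbalance, and no single primary adjusted analysis is fixed

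*SAP*

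**What the plan says.** **Entry rule.** SAP 3.8 compares baseline characteristics across the three cohorts. It treats as potential confounders "Variables for which a trend for statistical significance (P<0.15) or clinically important difference" (more than 2-fold) is found. Protocol 10.2 applies the same criterion and says that such variables "will be included in the multivariate analyses or propensity score development described later".

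**Aim.** Protocol 4.0 sets a different standard: "Statistical methods including multi-variate models and propensity scores will be used to adjust between group differences with respect to prognostic baseline characteristics".

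**Primary model.** SAP 3.10 analyses PGA 0 or 1 at six months by "simple logistic regression analysis and multivariate logistic regression models adjusting for potential confounders or the propensity score". The title of Table 49 in the SAP's list of tables repeats the choice between confounders and propensity scores. Neither names a covariate.

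**Method.** SAP 3.2 lists covariate adjustment, propensity scores and stratification, intends to explore all of them, and adds: "Unfortunately determination of the appropriate approach is data driven and cannot be determined a-priori".

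**Allowance.** The sample size is stated as "allowing for 100 additional patients (10 per variable) in the multivariate analysis", that is, ten variables. None is named.

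**Reporting and timing.** SAP 3.1.1 says: "Tables will include footnotes describing the analyses involved, and listings of covariates included in the analyses, where relevant". SAP 3.12 schedules analyses after 335 patients and after all patients have completed.

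**The concern.** Physicians choose the treatment, and SAP 3.2 ranks confounding by indication among the most important challenges. Baseline severity is an obvious candidate confounder, and baseline PGA is collected (Table 1 of both documents). Yet whether it enters the primary model depends on a significance test of cohort differences. That test does not ask whether a variable predicts response, so it does not deliver the prognostic adjustment promised in Protocol 4.0.

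The second gap is the open method. Several adjusted estimates of the primary comparison are permitted, and no rule says which one counts. The plan does not say whether the screen is run once or repeated, so the models at the 335-patient and final analyses could differ. Footnotes listing the covariates would report that choice without fixing it beforehand.

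**Working it through.** The plan gives no figure for the screen's behaviour, so there is none to reproduce.

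**1. Chance that the screen omits a factor**

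Inputs: cohorts 330:165:165 (Protocol 10.3, SAP 2.7) and entry at P<0.15 (SAP 3.8). Assumptions: a normal factor, one-way ANOVA, adalimumab shifted by d SD from both comparators, and the 2-fold limb not met.

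Adalimumab is half of the sample, so the noncentrality is 660 × (d/2)² = 165d². The omission probability is the noncentral F(2, 657) probability below the critical value of 1.90.

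| d (SD) | 165d² | Omitted, 330:165:165 | Omitted after 25% attrition |
|---|---|---|---|
| 0 | 0 | 0.85 | 0.85 |
| 0.10 | 1.65 | 0.63 | 0.68 |
| 0.15 | 3.71 | 0.40 | 0.50 |
| 0.20 | 6.60 | 0.20 | 0.30 |
| 0.30 | 14.85 | 0.02 | 0.06 |

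In this pattern an observed difference passes when 165d²/2 exceeds 1.90, so the threshold is d = √(2 × 1.90/165) = 0.152 SD.

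The 2-fold limb may not help baseline PGA. If all entrants score 3 to 5 (an assumption; Protocol 6.1.1 requires only moderate or severe disease by physician judgment), cohort means can differ by at most 5/3 = 1.67-fold.

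**2. Average bias from one screened factor**

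Simulation at n = 660, no true treatment effect, d = 0.15, and an assumed odds ratio of 1.5 or 2 per SD of the factor. The measure is the screened minus the always-adjusted log odds ratio.

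- OR 1.5 per SD: 0.012 to 0.013
- OR 2 per SD: 0.020 to 0.022

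exp(0.012) = 1.01 and exp(0.022) = 1.02. For scale, the plan's rates of 50%, 40% and 32% give these log odds ratios:

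- 50% v 40%: ln(1.5) = 0.405, so the bias is 0.012/0.405 = 3% to 0.022/0.405 = 5%
- 50% v 32%: ln(2.125) = 0.754, so the bias is 0.012/0.754 = 2% to 0.022/0.754 = 3%

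Type I error was 5.1% to 5.2% with the screen alone and 5.0% to 5.1% with the factor always included (4,000 runs). With stronger factors (OR 2 to 3 per SD, d 0.10 to 0.20; 1,500 runs) the screen gave 4.3% to 5.7%.

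**3. Forcing in a balanced prognostic factor**

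Simulation at 248:124:124 (after 25% attrition) with response rates of 50/40/32%.

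| Factor OR per SD | Change in SE of log OR | Squared z ratio, adjusted/unadjusted | Power, 50% v 40% |
|---|---|---|---|
| 1.5 | about +2% | 1.04 | 43.3% to 43.5% |
| 2 | about +6% | 1.10 | 44.9% to 48.0% |

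The standard error rises, so the interval for the log odds ratio does not narrow. The small power gain arises because the conditional odds ratio lies further from 1: at OR 2 per SD, the mean log odds ratio moved from 0.408 to 0.452 for 50% v 40%.

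**4. Room for a core set**

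Expected responders after 25% attrition: 247.5 × 0.50 + 123.75 × 0.40 + 123.75 × 0.32 = 213. An illustrative core has baseline PGA, BSA, age, sex, weight and disease duration (6 parameters), prior systemic, phototherapy and biologic use (3), and four regions (3), which is 12 parameters. Adding 2 for treatment gives 213/14 = 15 responders per parameter. At 335 patients (assumed 2:1:1, all evaluable): 167.5 × 0.50 + 83.75 × 0.40 + 83.75 × 0.32 = 144, and 144/14 = 10. Missing covariates would lower both figures.

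**The case against.** **The screen catches what matters.** The factors most tied to treatment choice should show large imbalances: Protocol 3.0 and 4.0 link adalimumab to failure of, or unsuitability for, earlier treatment. A 0.30 SD shift enters 98% of the time, and near-balanced factors confound little. This stands, and it limits the concern. A reader might infer that the primary result will be materially biased or its type I error inflated; the figures do not support that. An observed difference just under the threshold, with an odds ratio of 2 per SD, would give 0.152 × ln 2 = 0.105, or 26% of the 50% v 40% log odds ratio. That is a one-factor worst case, not an expected effect.

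**Always adjusting would sharpen the estimate.** A reader might infer this too. It does not hold for a logistic model: the standard error rises.

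**The rule bars nothing, and the table shells may list covariates.** SAP 3.8 says that screened variables go in, not that others stay out, and the body of Table 49 was not available. So one cannot say that baseline PGA is excluded, only that no available text guarantees it. SAP 3.2 expressly declines to settle the method in advance.

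**Adjustment in an observational study must respond to the data.** Partly so, but choosing core confounders needs no outcome data, and the screen can still add others.

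**Conclusion.** The concern holds in a limited form. The stated rule selects on imbalance alone, so baseline PGA is not guaranteed a place: omission is about 40% at 0.15 SD, 20% at 0.20 SD and 85% if balanced. With three adjustment methods left open, no single adjusted primary estimate is fixed. No figure here measures the effect of choosing among those methods; that part rests on the text.

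The numerical harm from the screen itself is small: a null odds ratio of about 1.01 to 1.02 for one factor at 0.15 SD, with type I error near 5%. The case for change is a fixed, reproducible primary analysis that meets the plan's own promise of prognostic adjustment, plus a small power gain. These sizes assume a normal factor, adalimumab shifted from both comparators, the planned cohort sizes, and odds ratios of 1.5 to 2 per SD, which the documents do not give. The change is advisable rather than essential.

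**What to change.** In SAP 3.8 and 3.10 and Protocol 10.2, before any outcome analysis:

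- State that baseline PGA always enters the primary adjusted model, with a short core set that the study team chooses on clinical grounds from data already collected. BSA, age, sex, weight, disease duration, prior treatment and region are examples, not a required list.
- Keep the P<0.15 or 2-fold screen only to add further factors. Run it once on baseline data and freeze the result. Protocol 6.2 says "Recruitment will be over a 24 month period"; if that holds, all patients are enrolled by the time the first completes 24 months, so the freeze can precede the 335-patient analysis.
- Designate one adjusted analysis as primary, for example the multivariable logistic regression in SAP 3.10. Report crude, propensity-score and stratified results as supportive.
- Use the same core set at the 335-patient and final analyses.
- Note that crude and adjusted odds ratios estimate different quantities.
- Check overlap between cohorts on prior-treatment factors. If it is poor, state the population to which the comparison applies.
- Give a rule for missing covariates.

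Cost: text changes, no new data and no change to the 660. The downsides are a few more parameters, a slightly larger standard error and the handling of missing covariates. At about 10 responders per parameter, a core of the illustrated size leaves little room for screened additions at the 335-patient analysis.
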